#### **10.2.5 Physical Examination**

A physician or suitably trained qualified assistant will perform a complete physical examination, including voluntary photography of skin lesions due to scratching, at Visits 1, 3, 6, and 9. A skin examination will be conducted at Visits 1, 3, 4, 6, 9, and 10 (see [Table 1](#)).

A complete physical examination will include assessment of general appearance, eyes, ears, nose, throat, head/neck/thyroid, lymph nodes, cardiovascular, lungs/chest, abdomen, genitourinary, extremities, skin, musculoskeletal, neurologic, and other.

Skin will be examined thoroughly and excoriations/scratch marks recorded.

#### **10.2.6 Vital Signs**

Evaluation of vital signs will be performed at all visits. This includes blood pressure (systolic and diastolic), pulse, respiratory rate, temperature, height (or length depending on age), and body weight (using a certified weight scale) at clinic visits. BMI will be calculated.

#### **10.2.7 Abdominal Ultrasound**

Ultrasound of the liver and spleen will be performed at randomization (Visit 3) and at EOT (Visit 9). Liver size, echogenicity, and presence of masses/nodules as well as spleen size will be recorded.

#### **10.2.8 Overdose**

A4250 is minimally absorbed and has a very low systemic availability. Based on toxicology data, for study purposes any dose exceeding a total of >3 mg/kg body weight of A4250 taken as a single dose or as a cumulative dose within 24 hours is defined as an overdose.

The no-adverse-effect dose level in the most sensitive species (defined as 20 mg/kg/day) in the rat 1 month toxicity study gives a human equivalent dose of approximately 194 mg/day in

a 60 kg person. This dose is approximately 10-fold higher than the maximum possible dose predicted in human studies (20 mg).

The investigator/investigative staff should immediately and not later than within 24 hours of knowledge of the overdose, be reported by the investigator or delegate on the SAE report form. In the event of an A4250 overdose, the patient should be monitored closely.

### **10.2.9 Pregnancy**

If a pregnancy is discovered in a female patient enrolled in the study before the end of dosing, the patient will be immediately discontinued from the study and will attend the same visits as a prematurely withdrawn patient. If the pregnancy is discovered in a female patient enrolled in the study after the end of dosing, the patient will continue in the study per protocol. If a pregnancy occurs in a male patient's partner at any time during the study, the pregnancy should also be reported and followed.

Pregnancy is not considered to be an AE. However, if the patient has been dosed with the study drug, the pregnancy must be reported on the Paper Pregnancy Notification Form immediately within 24 hours after recognition to Safety Manager (please refer to [Section 10.1.3](#)). Date of exposure and as far as possible, details of the period of gestation at the time of exposure must be given.

The pregnancy should be followed to determine outcome, including spontaneous termination, details of birth, and presence of any birth defects, congenital anomalies or newborn or maternal complication. The infant who was exposed in-utero will be followed for up to 2 years after delivery. Individual cases with an abnormal outcome in association with the study drug should be reported on an expedited basis, i.e., reported rapidly to a competent authority.

## **11 STATISTICAL EVALUATION**

All personnel involved with the analysis of the study will remain blinded until database lock for the double-blind Treatment Period and until major protocol violations have been identified.

All statistical analyses will be performed using SAS version 9.3 or higher.

### **11.1 Sample Size and Power**

For the EU and RoW, the primary analysis will relate to the serum bile acid responder endpoint. For the US, the primary analysis will relate to the pruritus endpoint. For each primary endpoint, a pooled analysis for the closed testing procedure will be applied to control the 1-sided overall type I error rate for two treatment comparisons vs. the placebo at the 0.025 level (Kane et al, 2015, Lehmacher et al, 1991, and Marcus et al, 1976). The study will enroll 60 to 70 patients in order to obtain at least 20 evaluable patients in each arm. For each primary endpoint, simulations with 5000 iterations using 20 patients per arm were conducted to estimate the power after multiplicity adjustment, resulting in a standard error of <0.7% for each estimated power.

Based on the Phase 2 A4250-003 study data both dose groups are predicted to have similar treatment effects for both serum bile acids and pruritus. For serum bile acids, simulated proportions were analyzed using the CMH test to generate the following 1-sided p-values: both A4250 arms pooled vs. placebo, low dose vs. placebo, and high dose vs. placebo. Assuming 60% responders in the A4250 arms and 10% responders in the placebo arm, the power to claim significance for a particular A4250 arm after multiplicity adjustment is approximately 94%. The power to claim significance for at least one arm or both arms are approximately 99% and 91%, respectively.

For the proportion of positive pruritus assessments at the subject level in pruritus scores, simulated proportions were analyzed using ANCOVA to generate the following 1-sided p-values: both A4250 arms pooled vs. placebo, low dose vs. placebo, and high dose vs. placebo. With an effect size of 1.0526, the simulated power to claim significance for a particular arm after multiplicity adjustment is approximately 89%. The probability to claim significance for at least one arm or both arms are approximately 95% and 83%, respectively.

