## 9 ASSESSMENT OF EFFICACY

### 9.1 Efficacy Endpoints

#### 9.1.1 Primary Efficacy Endpoint

The primary efficacy endpoints are as follows:

- **European Union (EU) and rest of the world (RoW):** Proportion of patients experiencing at least a 70% reduction in fasting s-BA concentration from baseline to the end of treatment or reaching a level  $\leq 70$   $\mu\text{mol/L}$  compared to placebo after 24 weeks of treatment.

Fasting s-BA baseline will be calculated as the average of the value at randomization and the previous visit (Clinic Visit 2). The end value is the average of the values at Weeks 22 and 24 after the start of double-blind treatment.

- **United States (US):** Proportion of positive pruritus assessments at the subject level over the 24-week Treatment Period. A positive pruritus assessment is defined as a scratching score of  $\leq 1$  or at least a one-point drop from baseline on the Albireo ObsRO instrument. At each assessment, the AM score will be compared to the baseline AM average, and the PM score will be compared to the baseline PM average. Both AM and PM pruritus assessments will be included in the analysis of this endpoint. AM scores from the 14 days prior to the first dose of study medications will be averaged as AM baseline. PM scores from the 14 days prior to the first dose will be averaged as PM baseline.

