## **11.2.2 Methods of Statistical Analyses**

### **11.2.2.1 General Principles**

The primary objective of this study is to show superiority in efficacy of A4250 (120 µg/kg/day and 40 µg/kg/day) compared to placebo in patients with PFIC Types 1 and 2.

In the EU and RoW, for the primary efficacy variable of fasting bile acid responder endpoint (at least a 70% reduction in fasting s-BA concentration or reaching a level  $\leq 70$  µmol/L at the end of treatment), the Cochran Mantel Haenszel (CMH) test stratified by PFIC class and age class will be performed to compare the proportion in fasting bile acid responder endpoint at the end of treatment (Week 22 and 24) in the two A4250 dose groups to placebo group. To ascertain that all data are used in the CMH analysis, neighboring strata will be pooled if all subjects in a stratum have the same response. Dropouts will be treated as non-responders. The proportion together with corresponding 95% CI, odds ratio and corresponding 95% Clopper-Pearson exact CI and p-value for the CMH test will be presented.

In the US, for the primary efficacy variable of the proportion of positive pruritus assessments at subject level over the 24-week treatment period, an analysis of covariance (ANCOVA) will be used. The model will include treatment arm, AM and PM baseline pruritus scores, and randomization stratification factors, i.e. PFIC class and age class. LS mean(SE) by treatment arm and LS mean difference (SE), 95% confidence intervals, and p-values (where applicable) between treatments (120 µg/kg/day and 40 µg/kg/day, respectively) vs. placebo will be provided. If there are concerns on model assumptions, i.e. normality and homogeneity of variances, a non-parametric ANCOVA based on the rank scores will be used as a sensitivity analysis. LS mean/SE on the outcome by treatment arm and LS mean difference/SE between active dose and placebo will be provided.

The procedure for multiplicity adjustment is specified as follows:

In the closed testing procedure, the low and high dose groups will be pooled to compare with the placebo group first. If the 1-sided p-value is  $\leq 0.025$ , the 1-sided p-values for low dose vs. placebo and high dose vs. placebo will be calculated, respectively. If both individual p-values are  $\leq 0.025$ , a significant treatment effect will be declared on both dose groups. If only one of them is  $\leq 0.025$ , a significant treatment effect will be declared on the corresponding dose group.

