#### **11.2.2.2 Missing Data**

In the primary analysis of the pruritus endpoint, all intermittently missing assessments will be classified as negative pruritus assessments. Similarly, all planned assessments after the intercurrent events (premature treatment discontinuation, death or initiation of rescue treatments such as biliary diversion surgery or liver transplantation) will be counted as negative pruritus assessments. However, as described above, all 336 assessments planned over the 24-week treatment period will be included in the denominator of the endpoint definition.

In the primary analysis of fasting bile acid responder endpoint, dropouts and patients with a missing average at the end of the treatment will be treated as non-responders. Patients in need of surgical rescue, i.e. biliary diversion and listing for liver transplant will be classified as non-responders. Continued collection of efficacy data for patients who discontinue treatment will be made as far as possible.

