### 11.1 Sample Size and Power

For the EU and RoW, the primary analysis will relate to the bile acid responder endpoint (at the 1-sided 1.25% level). For the US, the primary analysis will relate to the pruritus endpoint (at the 1-sided 1.25% level). The aim is to enroll 60 to 70 patients in order to get at least 60 evaluable patients.

Assuming 60% responders (patients experiencing at least 70% reduction in fasting s-BA concentration or reaching  $\leq 70$   $\mu\text{mol/L}$ ) in the A4250 dose group and 10% responders in the placebo group, approximately 20 patients per group are required to achieve a power of 84% with a 1.25% 1-sided Type-1 error.

For pruritus, with approximately 20 patients per treatment group, the power is 83% given an assumed treatment effect difference of -1.0 in change from baseline (-1.6 for A4250 and -0.6 for placebo) on the Albireo ObsRO scratching score with a SD of 0.95 and a Type I error of 1.25% (1-sided).

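### The 89% power stated for the US primary pruritus endpoint is not supported for the variable now tested: its effect size, 1.0526, matches the assumptions once made for a different endpoint, and no input on the proportion scale is given

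*Protocol*

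**What the plan says.** The current protocol defines the US primary endpoint in section 9.1.1 as "Proportion of positive pruritus assessments at the subject level over the 24-week Treatment Period". An assessment is positive if the scratching score is 1 or less, or at least one point below baseline, with AM and PM scores judged against separate baselines. Section 11.2.2.2 counts as negative every intermittently missing assessment and every planned assessment after discontinuation, death or rescue, and adds that "all 336 assessments planned over the 24-week treatment period will be included in the denominator of the endpoint definition".

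For power, section 11.1 states that "simulations with 5000 iterations using 20 patients per arm were conducted to estimate the power after multiplicity adjustment". The procedure is meant to "control the 1-sided overall type I error rate for two treatment comparisons vs. the placebo at the 0.025 level". Under section 11.2.2.1, "the low and high dose groups will be pooled to compare with the placebo group first", and each dose is then tested at the same level. For pruritus the section says: "With an effect size of 1.0526, the simulated power to claim significance for a particular arm after multiplicity adjustment is approximately 89" per cent; for at least one dose and for both doses it gives 95% and 83%.

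The same file holds earlier protocol versions. Section 11.1 of the 10 May 2018 version powered a different US primary endpoint, change in the worst-daily scratching score, "given an assumed treatment effect difference of -1.0 in change from baseline (-1.6 for A4250 and -0.6 for placebo"; its assumed SD was 0.95. The version dated 15 March 2018 uses the same two numbers.

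**The concern.** The effect size is attached to a proportion between 0 and 1, yet it equals to four decimals the ratio previously assumed for a change on a 0–4 scale. A standardised effect does not generally survive such a change of variable. The score has been dichotomised, and zeros are now added for missing and post-event assessments. A patient who leaves at Week 12 (under section 7.2.3, someone withdrawing for intolerable symptoms may then enter the open-label study) has at most 168 of 336 assessments that can be positive.

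Section 11.1 states nothing on the new scale: no mean proportion, SD, missing-entry rate or dropout rate. The bile acid paragraph beside it does state its inputs (60% and 10% responders). The Phase 2 pruritus result described in section 5.2.2 of the 10 May 2018 version is on a visual analogue scale, so it does not supply the effect size either.

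At stake is the only stated justification of 20 patients per arm for the US claim. The both-doses figure matters most, because section 11.2.2.1 frames the objective as superiority of both doses.

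**Working it through.** **1. Where 1.0526 may come from.** 1.0 / 0.95 = 1.05263, which rounds to 1.0526.

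**2. Reproducing the stated power.** Inputs: 20 per arm, standardised effect d = 1.0526 in both doses, pooled comparison at one-sided 0.025, then each dose at one-sided 0.025. With normal outcomes and 100,000 runs:

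| | One dose | At least one | Both |
|---|---|---|---|
| Stated | 89% | 95% | 83% |
| Three-group pooled variance | 90.0% | 95.9% | 84.1% |
| Separate two-sample t-tests | 89.6% | 95.8% | 83.4% |

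All are within about one point. The three figures follow from the effect size; only that input is in question. The earlier design also reproduces: 83.6% by noncentral t at one-sided 0.0125, against 83% stated.

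**3. What 1.0526 demands on the new scale.** Required difference in mean proportion = 1.0526 × SD: 0.21 for SD 0.20, 0.32 for SD 0.30, 0.42 for SD 0.40. The protocol states none of these.

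**4. Carrying the earlier assumptions through the new definition.** From the 10 May 2018 version: mean change −1.6 and −0.6, between-patient SD 0.95. Assumed here, because no document gives them: baseline mean 2.5 or 3.0 (SD 0.5, held within 2–4) and within-patient SD 0.3 to 1.0. Each of 336 scores is baseline + change + noise, rounded and held within 0–4. It is positive if it is 1 or less, or at least one point below baseline; 10% are then set to negative. One baseline serves AM and PM, and the full change is present from the start. Then d = (difference in mean proportions) / √(mean of the two variances).

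| Baseline mean | Within-patient SD | Mean proportion, A4250 / placebo | SDs | d | Power: one / at least one / both |
|---|---|---|---|---|---|
| 2.5 | 0.3 | 0.680 / 0.353 | 0.329, 0.377 | 0.93 | 81 / 90 / 72% |
| 3.0 | 0.3 | 0.640 / 0.328 | 0.350, 0.371 | 0.86 | 75 / 86 / 64% |
| 2.5 | 0.6 | 0.658 / 0.366 | 0.287, 0.319 | 0.96 | 83 / 92 / 75% |
| 3.0 | 0.6 | 0.631 / 0.331 | 0.295, 0.314 | 0.99 | 86 / 94 / 78% |
| 2.5 | 1.0 | 0.624 / 0.384 | 0.236, 0.259 | 0.97 | 85 / 93 / 77% |
| 3.0 | 1.0 | 0.604 / 0.356 | 0.240, 0.253 | 1.01 | 87 / 94 / 80% |

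For the third row: 0.292 / √((0.287² + 0.319²)/2) = 0.292 / 0.303 = 0.96.

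**5. Wider assumptions.** With baseline mean 2.5–3.4 and within-patient SD 0.3–0.9, d is about 0.9–1.0 for full diaries without dropout, and about 0.86–0.96 with 10% missing entries and 10% dropout. The closed test at 20 per arm gives 79 / 88 / 69% at d = 0.9 and 87 / 94 / 79% at d = 1.0. The range 0.86–0.96 corresponds to roughly 75–84% per dose and 64–76% for both.

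**The case against.** The strongest case on the other side has four parts.

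- **The origin is inferred.** 1.0526 also equals 0.20/0.19, a plausible pair on a 0–1 scale. Section 11.1 says proportions were simulated, and bounded (beta) proportions with means 0.30 and 0.50 and SD 0.19 give 89.1 / 95.2 / 83.1%, at least as close to the stated figures as a normal score. This stands: the power figures do not show which variable was simulated. A reader might infer from the match that the carry-over is established; the documents do not say so.
- **The earlier versions are superseded, and the inputs may be recorded elsewhere.** A difference from superseded text is not an error, and it is used here only to suggest a source. The SAP and the front part of the current version were not available. But section 11.1 itself attaches three power figures to this endpoint, so the gap is in a statement the protocol makes, not in a detail it defers.
- **The shortfall rests on assumed inputs.** This is true, and the upper end of the full-diary case comes close to the stated figures. A reader might infer that the true power is known to be below 89%; it is not.
- **There are offsets.** The planned ANCOVA adjusts for baseline pruritus, PFIC class and age class. A covariate correlation of 0.3–0.4 (assumed) would raise d = 0.96 to 0.96/√(1 − 0.09) = 1.01 or 0.96/√(1 − 0.16) = 1.05. Enrolment may reach 70, about 23 per arm, which gives 89 / 95 / 82% at d = 0.96 and 82 / 91 / 73% at d = 0.87. Both could recover part or all of the loss, but section 11.1 claims its power at 20 per arm and credits neither.

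**Conclusion.** The stated 89%, 95% and 83% are not supported for the endpoint now tested. Given d = 1.0526 they are right, so this is not an arithmetic error. The weakness is that the effect size has no stated basis on the proportion scale, appears to come from another variable, and carries no stated allowance for the missing-equals-negative rule.

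On the sponsor's own earlier score assumptions the figures are probably somewhat optimistic. With 10% missing entries and 10% dropout, power is roughly 75–84% per dose against 89%, and 64–76% for both doses against 83%. This is at 20 per arm before covariate adjustment, and depends on the assumed baseline mean, within-patient SD, missingness and dropout. The proportion could have a standardised effect near 1.05; true power is unknown.

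The point concerns the justification of the trial's size. It does not touch the validity of the planned test, its error control or the endpoint definition.

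**What to change.** Rewrite the pruritus paragraph of section 11.1. State the assumed mean proportion of positive assessments in each arm, its SD, the expected missing-entry and dropout rates, and the source of each. Rerun the closed-test ANCOVA simulation on subject-level proportions out of 336, with missing, post-discontinuation and post-rescue assessments set to negative, over a range of inputs. Restate the three power figures from that run, and say whether covariate adjustment and enrolment above 60 are counted. If 1.0526 was derived on the proportion scale, showing the means and SD behind it, with the allowance for missing and post-event assessments, would settle the question of its source.

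The cost is one simulation, one revised paragraph and possibly a less favourable stated power. No change in sample size is needed.

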### **11.2 Statistical Methods**

#### **11.2.1 Statistical Analysis Sets**

##### **Safety Analysis Set**

The safety analysis set will consist of all patients who received at least 1 dose of study drug. Patients will be analyzed according to the treatment they actually received. The safety analysis set will be the primary analysis set for safety analyses.

##### **Full Analysis Set**

The full analysis set (FAS) will consist of all randomized patients who received at least 1 dose of assigned treatment. Patients will be analyzed in the treatment group they were randomized to even if they received incorrect study drug. The FAS will be the primary analysis set for efficacy analyses.

### **Per Protocol Analysis Set**

The per protocol (PP) analysis set is a subset of the FAS, and will consist of all randomized patients for whom no major protocol violation (no violation which may affect the study efficacy outcome) is documented. The PP analysis set will provide supportive data for the efficacy analyses.

Allocation of patients to the PP analysis set will be performed before unblinding of the study.

## **11.2.2 Methods of Statistical Analyses**

### **11.2.2.1 General Principles**

The primary objective of this study is to show superiority in efficacy of A4250 (120 µg/kg/day and 40 µg/kg/day) compared to placebo in patients with PFIC Types 1 and 2.

In the EU and RoW, for the primary efficacy variable of fasting bile acid responder endpoint (at least a 70% reduction in fasting s-BA concentration or reaching a level  $\leq 70$  µmol/L at the end of treatment), the Cochran Mantel Haenszel (CMH) test stratified by PFIC class and age class will be performed to compare the proportion in fasting bile acid responder endpoint at the end of treatment (Week 22 and 24) in the two A4250 dose groups to placebo group. To ascertain that all data are used in the CMH analysis, neighboring strata will be pooled if all subjects in a stratum have the same response. Dropouts will be treated as non-responders. The proportion together with corresponding 95% CI, odds ratio and corresponding 95% Clopper-Pearson exact CI and p-value for the CMH test will be presented.

In the US, for the primary efficacy variable of the proportion of positive pruritus assessments at subject level over the 24-week treatment period, an analysis of covariance (ANCOVA) will be used. The model will include treatment arm, AM and PM baseline pruritus scores, and randomization stratification factors, i.e. PFIC class and age class. LS mean(SE) by treatment arm and LS mean difference (SE), 95% confidence intervals, and p-values (where applicable) between treatments (120 µg/kg/day and 40 µg/kg/day, respectively) vs. placebo will be provided. If there are concerns on model assumptions, i.e. normality and homogeneity of variances, a non-parametric ANCOVA based on the rank scores will be used as a sensitivity analysis. LS mean/SE on the outcome by treatment arm and LS mean difference/SE between active dose and placebo will be provided.

The procedure for multiplicity adjustment is specified as follows:

In the closed testing procedure, the low and high dose groups will be pooled to compare with the placebo group first. If the 1-sided p-value is  $\leq 0.025$ , the 1-sided p-values for low dose vs. placebo and high dose vs. placebo will be calculated, respectively. If both individual p-values are  $\leq 0.025$ , a significant treatment effect will be declared on both dose groups. If only one of them is  $\leq 0.025$ , a significant treatment effect will be declared on the corresponding dose group.

Other secondary and exploratory outcome variables will provide supportive efficacy and safety information regarding the differences between the treatment groups. No adjustments will be performed for multiple comparisons when testing secondary and exploratory efficacy variables.

If not otherwise specified, the baseline value of a parameter is defined as the last assessment of that parameter prior to the first intake of study treatment.

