#### 8.3.3 Blinding and Randomization of Study Drug

A double-blind design is employed so that both the investigators and the patients will be unaware of the treatment assignment during the study.

After written informed consent is obtained from an eligible patient, an 8-digit patient identification number will be assigned. The first 2 digits will denote the country, followed by a 3-digit site number and a 3-digit patient sequence number. This number will be created and

allocated by the Interactive Web Response System (IWRS), when the patient first enters the system at Screening. The randomization codes will be computer-generated by [REDACTED] Biostatistics, and kept by a statistician independent from the project team. The randomization will be done in blocks and stratified according to PFIC class (Type 1 and 2) and age class (6 months to 5 years, 6 to 12 years, and 13 to  $\leq 18$  years) to ensure approximate balance between dose schemes (1:1:1). A separate randomization list will be prepared for the maximum 5 patients from Study A4250-003 regardless of stratification. Randomization codes will be assigned sequentially as patients become eligible for randomization.

Patients who are eligible for randomization will be assigned a unique 4-digit randomization number by IWRS. This randomization number identifies which treatment will be allocated to the patient. Patients who withdraw from the study after randomization visit are not to be replaced and their randomization number will not be reused.

To ensure blinding, the study drug and the matching placebo have the same shape and size. Patients will receive capsule(s) of A4250 according to their dose group or capsule(s) of matching placebo once a day during the double-blind Treatment Period. Labels on the study drug containers will not identify the treatment that a patient is randomized to. Traceability of the treatment is ensured by the study drug number.

The 5-digit study drug number will identify study drug packs and will be detailed on the study drug label. Dispensing of study drug will be coordinated by IWRS.

The system will assign a study drug number corresponding to the randomization arm. The randomization number will be used in the background only to ensure no unblinding and will not be displayed to end-users in the IWRS.

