#### 9.1.2 Secondary Efficacy Endpoint

Secondary efficacy endpoints include the following:

- **EU and RoW:** Proportion of positive pruritus assessments at the subject level over the 24-week Treatment Period. A positive pruritus assessment is defined as a scratching score of  $\leq 1$  or at least a one-point drop from baseline on the Albireo ObsRO instrument. At each assessment, the AM score will be compared to the baseline AM average, and the PM score will be compared to the baseline PM average. Both AM and PM pruritus assessments will be included in the analysis of this endpoint. AM scores from the 14 days prior to the first dose of study medications will be averaged as AM baseline. PM scores from the 14 days prior to the first dose will be averaged as PM baseline.
- **US:** Proportion of patients experiencing at least a 70% reduction in fasting s-BA concentration from baseline to the end of treatment or reaching a level  $\leq 70$   $\mu\text{mol/L}$  compared to placebo after 24 weeks of treatment.
- **All Regions:**

All secondary endpoints are compared to placebo.

- Change from baseline to Week 12 and to Week 24 in fasting serum bile acids
- Change from baseline to Week 12 and to Week 24 in serum ALT concentration
- Change in growth from baseline to Week 12 and to Week 24
- Proportion of responders for pruritus scores at Weeks 12 and 24 based on the Albireo PRO and ObsRO instruments
- Change in sleep parameters measured with the Albireo PRO and ObsRO instruments from baseline over the 24-week Treatment Period
- Proportion of individual assessments meeting the definition of a positive pruritus assessment at the subject level over the 24-week Treatment Period. A positive pruritus assessment includes an itch score  $\leq 1$ , or at least a one-point drop from baseline based on the Albireo PRO instrument; only patients  $\geq 8$  years of age will complete the Albireo PRO instrument
- Proportion of individual assessments meeting the definition of a positive pruritus assessment at the subject level from Weeks 0-4, Weeks 0-8, Weeks 0-12, Weeks 0-18, Weeks 0-24, respectively, or the proportion of positive pruritus assessments at each 4-week interval.
- Proportion of individual AM assessments meeting the definition of a positive pruritus assessment at the subject level from Weeks 0-4, Weeks 0-8, Weeks 0-12, Weeks 0-18, Weeks 0-24, respectively, or the proportion of positive pruritus assessments at each 4-week interval.

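### Within each region the plan has no testing hierarchy from its primary endpoint to the other region's primary endpoint, so only one of the two endpoints the trial is powered for can be confirmed there

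*Protocol*

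**What the plan says.** Section 11.1 makes s-BA response primary for the EU and rest of world (RoW) and pruritus primary for the US. Multiplicity is handled one endpoint at a time: "For each primary endpoint, a pooled analysis for the closed testing procedure will be applied", in order to "control the 1-sided overall type I error rate for two treatment comparisons vs. the placebo at the 0.025 level". Section 11.2.2.1 gives the steps: "In the closed testing procedure, the low and high dose groups will be pooled to compare with the placebo group first". If that 1-sided p-value is at most 0.025, each dose is compared with placebo, again at 0.025.

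Section 9.1.2 then lists the other region's primary first among the secondaries. For EU/RoW this is "Proportion of positive pruritus assessments at the subject level over the 24-week Treatment Period"; for the US it is the s-BA responder proportion. Section 11.2.2.1 describes other secondary and exploratory variables as supportive and adds "No adjustments will be performed for multiple comparisons when testing secondary and exploratory efficacy variables". The current text shown contains no rule that links the primary endpoint to this secondary.

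**The concern.** The two endpoints do not have the same standing as the rest of the secondary list. Section 11.1 reports simulated power for both with 20 patients per arm, and each carries the primary decision in one region. Within a region, however, the second endpoint is treated like any exploratory variable: whatever its result, it stays nominal. Nothing is wrong with supportive secondaries in general. The issue is that this one endpoint could have been made confirmatory after the primary, with the plan's own procedure, without taking alpha from the primary. If someone later reads its nominal p-value as a claim, the error rate over the two endpoints is above 0.025.

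**Working it through.** **Inputs.**
- Alpha 1-sided 0.025 for the two dose comparisons on a primary endpoint (section 11.1).
- Three arms of 20 (section 11.1: "simulations with 5000 iterations using 20 patients per arm were conducted"), allocated "to ensure approximate balance between dose schemes (1:1:1") (section 8.3.3).
- s-BA responders 60% on each dose and 10% on placebo; pruritus effect size 1.0526 (section 11.1).
- Assumed, because the protocol gives neither: the level for the secondary tests (1-sided 0.025) and the within-patient correlation between endpoints (0 to 0.8 for error rates, 0 to 0.6 for power).

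**The plan's own figures first.** Single-dose power before the pooled step, normal approximation:
- Pruritus: 1.0526/√(2/20) = 3.329; 3.329 − 1.960 = 1.369; Φ(1.369) = 91.4%.
- s-BA: pooled rate 0.35, so the null SE is √(2×0.35×0.65/20) = 0.1508. The alternative SE is √((0.24+0.09)/20) = 0.1285. (0.5 − 1.96×0.1508)/0.1285 = 1.59; Φ(1.59) = 94.4%.

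Simulating the full closed test gives, for a particular dose / at least one dose / both doses:
- s-BA 94.9 / 98.4 / 91.5%, against the stated 94 / 99 / 91%.
- Pruritus 89.9 / 95.9 / 84.1%, against the stated 89 / 95 / 83%.

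All six agree within 2 points.

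**Error on the second endpoint alone, raw dose tests.** The shared placebo arm gives a correlation of 0.5 between the two dose statistics: 1 − P(Z₁<1.96, Z₂<1.96) = 4.54%. If they were independent it would be 1 − 0.975² = 4.94%.

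**Error across primary and second endpoint** (simulated; closed test on the primary throughout; configurations: no effect anywhere, and one dose active on the primary only):

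| Handling of the second endpoint | Family-wise error |
|---|---|
| Raw dose tests, no gate | about 5.5-6.9% |
| Closed test, no gate | about 3.5-4.7% |
| Closed test, only after both doses win on the primary | about 2.5% or less |
| Dose-by-dose gate at full alpha, closed test, one dose clearly active on the primary | about 3.5-3.8% |
| Dose-by-dose gate at full alpha, raw dose tests | up to about 4.9% |

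Why the both-doses gate works: if any primary null hypothesis is true, the gate can open only by rejecting it, which is already counted within 0.025. If none is true, the only possible errors are on the second endpoint, where the closed test holds 0.025.

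**Power behind the gate.** At correlation 0 it is a product of the simulated powers.
- EU/RoW pruritus: gate 0.915; a particular dose 0.915×0.901 = 82.4%; both doses 0.915×0.842 = 77.0%.
- US s-BA: gate 0.842; a particular dose 0.842×0.949 = 79.9%; both doses 0.842×0.915 = 77.0%.

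Over correlations of 0 to 0.6 the ranges are 82-84% and 80-81% for a particular dose, and 77-79% for both doses in either region. The plan's own rounded powers give slightly less at correlation 0: 0.91×0.89 = 81% and 0.83×0.94 = 78%.

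**The case against.** A reader might infer that the plan breaks its own type I error promise, or that the second endpoint is tested with no error control at all. The documents support neither.
- Section 11.1 promises 0.025 only for the two dose comparisons on each primary endpoint, and the closed test delivers that.
- The closed test will be run on both s-BA and pruritus, since each is primary somewhere. Closed-test dose decisions will therefore exist for both, and no separate unadjusted re-analysis under the secondary label is specified. That is why 3.5-4.7% is the fairer figure if those results are reused; 5.5-6.9% applies only if raw dose tests are read as claims.
- The protocol states no level and no claim rule for secondaries. Calling them supportive is coherent, and family-wise error is at stake only if a claim is made.

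All of this stands, and it makes the point an improvement and not an error. What remains is that control over doses within one endpoint is not a hierarchy between two endpoints, and that the no-adjustment sentence excludes such a hierarchy.

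Two uncertainties also remain. The paragraph opens by speaking of other secondary variables, which could hint at separate handling of the main one, but its next sentence covers secondary variables without exception. In addition, the first part of the current protocol, with its synopsis, and the SAP are not shown; a gate placed there would conflict with section 11.2.2.1. The superseded version dated 10 May 2018 gated this endpoint, but a difference from superseded text is no error and nothing here rests on it.

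**Conclusion.** The point holds as a missed improvement. In each region the plan can confirm one of the two endpoints it is powered for, because the other is exempted from any adjustment and no rule leads to it from the primary. The error figures are conditional on someone claiming the second endpoint at an assumed 1-sided 0.025, and they vary with the unknown endpoint correlation. The power figures rest on the plan's 60%/10% responder rates and effect size of 1.0526 with 20 patients per arm. The benefit should not be read as the gate-opening probability (about 91% and 83% on the plan's figures): the gated chance for a particular dose is lower, and below the ungated single-dose powers of 91.4% and 94.4%. The gate is free for the primary test only.

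**What to change.** In section 11.2.2.1, exempt this one endpoint from the no-adjustment sentence. State that in each region, only if both doses are significant on the primary endpoint, the other region's primary endpoint is tested with the same pooled-then-individual closed procedure at 1-sided 0.025. Otherwise it is reported descriptively, and all remaining secondaries stay supportive. Repeat the rule in the SAP before unblinding.

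Do not open the gate dose by dose, or after a win on either dose, at full alpha: neither form holds 0.025, and each would need an alpha split.

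The cost is a sentence in each document. No extra data are needed and the primary analysis and its power do not change. If fewer than both doses win on the primary, the second endpoint stays descriptive, which is in effect its present status.
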